8.2 Handling of Missing Data

The analysis will be based on As Observed data, and no imputation will be conducted.

8.3 Primary Efficacy Endpoint and Analyses

There are no primary efficacy endpoints or analyses for this study.

8.4 Secondary Efficacy Analyses

Descriptive statistics will be provided for each treatment group for all visits. These include the number of observations, mean with 95% confidence interval, standard deviation, median, minimum and maximum for continuous endpoints and count endpoints; and frequencies and percentages with 95% confidence interval for binary endpoints.

No missing data imputation will be applied. All efficacy analyses will be based on As Observed (AO) analysis, and thus a subject who does not have an evaluation at the primary analysis time point will not be included.

8.5 Additional Efficacy Analyses

No additional efficacy analyses are planned.

8.6 Efficacy Subgroup Analyses

No subgroup analyses will be performed.

9.0 Safety Analyses

9.1 General Considerations

Safety analyses will include reporting of adverse events, laboratory, and vital signs measurements based on data in Study M20-186. Safety analyses will be carried out using the Safety Analysis Set.

The following summary statistics will be presented for subjects who have both baseline and post-baseline values for laboratory parameters and vital signs: the mean value at Baseline and at each respective protocol specified visit, and the mean, standard deviation and median for changes from Baseline. Categorical data will be summarized using frequencies and percentages. The number of non-missing values will be given. Missing safety data will not be imputed.

For safety analysis, Baseline is defined as the last available measurement before Study M19-130 study drug administration if the subjects took active treatment in Study M19-130, and the last available measurement before Study M20-186 study drug administration if the subjects took placebo in Study M19-130.

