9.2.1 Treatment-Emergent Adverse Events

To summarize data from Study M20-186, a treatment-emergent Adverse Event (TEAE) is defined as an adverse event with an onset date that is on or after the first dose of study drug from Study M20-186, and no more than 30 days after the last dose of study drug from Study M20-186.

Events where the onset date is the same as Study M20-186 study drug start date are assumed to be treatment-emergent, unless the Study M20-186 study drug start time and the adverse event start time are collected and the adverse event start time is prior to the Study M20-186 study drug start time. If an incomplete onset date was collected for an adverse event, the event will be assumed to be treatment-emergent unless there is other evidence that confirms that the event was not treatment-emergent (e.g., the event end date was prior to the study drug start date). All treatment-emergent AEs will be summarized overall, as well as by primary MedDRA SOC and Preferred Term. The SOCs will be presented in alphabetical order, and the PTs will be presented in alphabetical order within each SOC.

The number and percentage of subjects experiencing TEAEs will be summarized.

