9.3 Analysis of Laboratory Data

Data collected from central and local laboratories, including additional laboratory testing due to an SAE, will be used in all analyses, except for Baseline, where SAE-related laboratory assessments on or before the first dose of study drug will be excluded. The clinical laboratory tests defined in the protocol operations manual (e.g., hematology and clinical chemistry) will be summarized.

Each laboratory variable will be summarized for all time points (starting with Baseline) with the number of non-missing observations, mean and standard deviation, median, minimum and maximum.

Mean change from Baseline to each applicable post-Baseline visit will be summarized for selected laboratory variables, with the number of observations, Baseline mean, and visit mean, at each visit in Study M20-186 for each treatment group. The change from Baseline mean, standard error, and 95% confidence interval will be presented for the mean change from Baseline within each treatment group.

Shift tables will be provided for each hematology, clinical chemistry parameter. Shifts from Baseline to the following endpoints will be considered: post-Baseline value and final value. This analysis will be performed only for category of "low or normal" at Baseline which shift to 'high' and category of "high or normal" at Baseline which shift to category of 'low.'

For selected laboratory variables including hemoglobin, neutrophils, lymphocytes, platelets, creatinine, ALT, AST, CPK, LDL cholesterol, HDL cholesterol, total cholesterol, and triglycerides, a listing of all observations collected will be generated for subjects that had at least one post-Baseline observation meeting pre-defined criteria for potentially clinically important values. The number and percentage of subjects in each treatment group who have at least one post-Baseline observation meeting the pre-defined criteria for potentially clinically important values will be provided for each variable. The criteria for potentially clinically important laboratory values will be determined by NCI CTCAE version 4.03 of greater than Grade 3 or greater than Grade 4.

For the purpose of assessing for potential Hy's law cases, the frequencies and percentages of subjects with post baseline liver-specific function test values that meet the following criteria of potential clinical interest will be summarized by "as treated" treatment group:

- $ALT \geq 3 \times ULN$
- $ALT \geq 5 \times ULN$

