13.0 Version History

Table 1. SAP Version History Summary

Version	Date	Summary
1.0	12 August 2020	Original version
2.0	02 January 2024	
1. Updated to align with the updates in the protocol after M19-130 interim analysis.2. Update analysis of study drug duration and analysis of safety to use M20-186 data only. Integrated data will be summarized later in the submission of SLE Phase 3 program.

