Appendix C. Potentially Clinically Important Criteria for Vital Sign Values

Vital Sign	Category	Criteria for Potential Clinically Important Vital Signs
Systolic blood pressure	Low	Value \leq 90 mmHg and decrease \geq 20 mmHg from Baseline
	High	Value \geq 160 mmHg and increase \geq 20 mmHg from Baseline
Diastolic blood pressure	Low	Value \leq 50 mmHg and decrease \geq 10 mmHg from Baseline
	High	Value \geq 100 mmHg and increase \geq 10 mmHg from Baseline
Weight	High	> 7% increase from baseline
	Low	> 7% decrease from baseline

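### For Groups 1-4, M20-186 laboratory shift and vital-sign PCI counts run from the pre-drug M19-130 Baseline and do not separate new cases from changes carried over from M19-130

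*SAP*

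**What the plan says.** **Data window.** SAP 9.1 describes the safety analyses as "reporting of adverse events, laboratory, and vital signs measurements based on data in Study M20-186". The entry for version 2.0 in SAP 13.0 records the change: "Update analysis of study drug duration and analysis of safety to use M20-186 data only". The same entry defers integrated summaries to a later submission.

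**Reference point.** SAP 9.1 sets two safety Baselines. For Groups 1-4, "Baseline is defined as the last available measurement before Study M19-130 study drug administration if the subjects took active treatment in Study M19-130". For Groups 5a/5b it is "the last available measurement before Study M20-186 study drug administration if the subjects took placebo in Study M19-130". In both cases this is the last value before first active drug.

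**Outputs that use it.**
- Laboratory shift tables (SAP 9.3): "Shifts from Baseline to the following endpoints will be considered: post-Baseline value and final value".
- Mean changes by visit (SAP 9.3 and 9.4).
- Vital-sign PCI criteria (SAP 9.4 and Appendix C). The high-weight criterion is simply "> 7% increase from baseline", with a mirror-image criterion for loss. The blood-pressure criteria combine a change with an absolute value.

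**Outputs that do not.**
- A treatment-emergent event needs "an onset date that is on or after the first dose of study drug from Study M20-186" (SAP 9.2.1).
- Laboratory PCI criteria are "determined by NCI CTCAE version 4.03 of greater than Grade 3 or greater than Grade 4" (SAP 9.3).
- The liver criteria for Hy's law are multiples of the upper limit of normal.

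Neither SAP 9.3 nor 9.4 excludes or marks subjects who already met a shift or PCI criterion on entering M20-186.

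**The concern.** The primary objective is longer-term safety, and Protocol 4.2 makes each group's own safety profile in M19-130 the main comparator. A reader of the M20-186 report will want to know what happened after Week 48.

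The tables answer that in two ways. A laboratory abnormality that began at Week 12 of M19-130 and never resolved is not an M20-186 treatment-emergent event, but it is counted in the M20-186 shift table. A Group 1 subject who gained 8% in weight by Week 48 and then stayed level is an M20-186 weight PCI case, although nothing changed in M20-186. The shift and PCI counts cannot show whether a case is a stable first-year effect or something that emerged with continued dosing.

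**Working it through.** **1. The plan's own figures.** M19-130 projects 5 groups of 65: 5 × 65 = 325. Rollover of 60% to 80% gives 0.60 × 325 = 195 and 0.80 × 325 = 260, as stated in Protocol 7.7 and SAP 2.4. If rollover is even and all groups continue, Groups 1-4 have 0.60 × 65 = 39 to 0.80 × 65 = 52 subjects each; 5a and 5b have half of that, about 20 to 26 each. The treatment period is 104 − 48 = 56 weeks, as stated.

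**2. Weeks from safety Baseline to each visit (SAP 9.1 applied to the visit schedule).**

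| Visit week | 56 | 64 | 72 | 80 | 88 | 96 | 104 |
|---|---|---|---|---|---|---|---|
| Groups 1-4 | 56 | 64 | 72 | 80 | 88 | 96 | 104 |
| Groups 5a/5b | 8 | 16 | 24 | 32 | 40 | 48 | 56 |

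The pairs on the same extension regimen (1 with 5a, 2 with 5b) are 48 weeks apart at every visit.

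**3. What is counted in Groups 1-4.**
- Arose in M19-130, resolved there and did not recur: not counted, because only M20-186 data enter.
- Arose in M19-130 and persists or recurs at an M20-186 visit: counted.
- Arose in M20-186: counted, and not distinguishable from the previous case.

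**4. Illustration for laboratory shifts (all rates assumed).** Let r be a constant annual risk of shift, and f the fraction of M19-130 shifts still present in M20-186.
- p48 = 1 − (1 − r)^(48/52)
- pLTE = 1 − (1 − r)^(56/52)
- carried = p48 × f
- counted = carried + (1 − carried) × pLTE

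For r = 10%, f = 50%: p48 = 0.0927, pLTE = 0.1073, carried = 0.0463, and counted = 0.0463 + 0.9537 × 0.1073 = 0.149. The carried share is 0.0463 / 0.149 = 31%. In a group of 39 to 52 that is about 1.8 to 2.4 of 5.8 to 7.7 counted subjects.

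| r | f | Counted | Arising in M20-186 | Carried share |
|---|---|---|---|---|
| 5% | 25% | 6.5% | 5.3% | 17.9% |
| 5% | 100% | 9.8% | 5.1% | 47.4% |
| 10% | 50% | 14.9% | 10.2% | 31.2% |
| 20% | 25% | 25.0% | 20.4% | 18.6% |
| 20% | 100% | 36.0% | 17.4% | 51.7% |

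**5. Illustration for weight gain above 7% (all inputs assumed).** Percent weight change is simulated as a zero-drift random walk with the annual SD shown and 1-point measurement noise, over seven M20-186 visits, in 400,000 subjects.

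| Annual SD | Any visit >7%, M19-130 Baseline | Any visit >7%, LTE Baseline | Of those flagged from M19-130 Baseline: already met at Week 48 | Of those flagged from M19-130 Baseline: never >7% from LTE Baseline |
|---|---|---|---|---|
| 3 | 10.3% | 3.3% | 11.9% | 82.3% |
| 5 | 26.0% | 15.0% | 28.0% | 62.6% |
| 7 | 36.4% | 26.6% | 39.1% | 50.5% |

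A second model takes the Week 48 change as normal with (mean, SD) of (0, 4), (1.5, 4.5) and (3, 5), then a zero-drift walk. It gives 17.2%, 29.8% and 42.4% from M19-130 Baseline, against 7.2%, 10.0% and 12.8% from LTE Baseline.

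The last two columns of the table answer different questions. Some subjects cross 7% during M20-186 on the strength of a gain begun in M19-130. They are new to the criterion, but most of the change may be old. A Week 48 flag therefore does not replace tables from LTE Baseline.

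**The case against.** **The Baseline rule is coherent.** It gives every group the same kind of reference, the last value before active drug, and keeps Groups 1-4 on one scale with their M19-130 results, which suits the comparison in Protocol 4.2. Version 2.0 restricts the data, and that does not oblige the reference point to move. This stands: the rule is not an error and should stay.

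**The course after Week 48 is partly visible.** SAP 9.3 and 9.4 give summaries by visit, so a plateau or a drift from Week 56 to Week 104 would show at group level. Listings cover subjects with laboratory or vital-sign PCI values. A reader might infer that nothing planned shows change after Week 48; the documents do not support that. The gap is in the shift and PCI counts, which means do not fill and which listings fill only case by case.

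**The scope is limited.** Adverse events, serious events, events of special interest and deaths are unaffected. Laboratory PCI and Hy's law criteria are not written as change from Baseline, and blood-pressure PCI also needs an absolute value at the visit. This stands.

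**Same-regimen groups.** A reader might infer that the Baseline rule makes Groups 1 and 5a (or 2 and 5b) impossible to read together, and that LTE Baseline for all would cure it. Neither follows. The 48-week gap comes from the rollover design, the group labels state the treatment sequence, and no between-group safety contrast is planned. LTE Baseline would equalise the interval but set an on-drug starting value in Groups 1/2 against a drug-free one in 5a/5b. A first-year drug effect would vanish from one and appear in full in the other.

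**Conclusion.** The point holds in a limited form. For Groups 1-4, M20-186 laboratory shift counts and vital-sign PCI counts, weight above all, include changes from M19-130 that persist or recur, and no planned count tells them from new ones. Mean changes have the same reference, but the visit summaries soften the problem there. The mechanism follows from the SAP text and needs no assumption.

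The size does. On the assumed rates above, about 18% to 52% of counted laboratory shifts would be carried over. Weight flags would run at 10% to 42% from M19-130 Baseline against 3% to 27% from LTE Baseline. The documents give no shift rates, persistence or weight variability, so these are illustrations and not estimates. The weight figures should not be read across to shifts or blood pressure.

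This is a gap in a descriptive display that is cheap to close. It does not undermine the adverse-event analyses.

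**What to change.** 1. In SAP 9.1, keep the present Baseline and all its tables, and define LTE Baseline as the last value before the first M20-186 dose.
2. In SAP 9.3 and 9.4, mark in the Group 1-4 shift and PCI tables the subjects who already met the criterion at LTE Baseline, so that each count splits into already met and newly met.
3. Add supplementary shift, mean-change and PCI tables for Groups 1-4 from LTE Baseline.
4. Label time since first active drug on outputs that show Groups 1/2 with 5a/5b, and state that LTE Baseline is not the common reference for comparing those groups.

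The cost is SAP wording and a rerun of existing tables. Laboratory tests, vital signs and weight at Week 48 are already in the activity schedule (Protocol Appendix D), so no new data are needed. The downside is more output.

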9.2 Adverse Events

Adverse events (AEs) will be summarized and presented using primary MedDRA System Organ Classes (SOCs) and preferred terms (PTs) according to the version of the MedDRA coding dictionary used for the study at the time of database lock. The actual version of the MedDRA coding dictionary used will be noted in the AE tables and in the clinical study report. Specific adverse events will be counted once for each subject for calculating percentages, unless stated otherwise. In addition, if the same adverse event occurs multiple times within a subject, the maximum toxicity grade and level of relationship to investigational product will be reported.

9.2.1 Treatment-Emergent Adverse Events

To summarize data from Study M20-186, a treatment-emergent Adverse Event (TEAE) is defined as an adverse event with an onset date that is on or after the first dose of study drug from Study M20-186, and no more than 30 days after the last dose of study drug from Study M20-186.

Events where the onset date is the same as Study M20-186 study drug start date are assumed to be treatment-emergent, unless the Study M20-186 study drug start time and the adverse event start time are collected and the adverse event start time is prior to the Study M20-186 study drug start time. If an incomplete onset date was collected for an adverse event, the event will be assumed to be treatment-emergent unless there is other evidence that confirms that the event was not treatment-emergent (e.g., the event end date was prior to the study drug start date). All treatment-emergent AEs will be summarized overall, as well as by primary MedDRA SOC and Preferred Term. The SOCs will be presented in alphabetical order, and the PTs will be presented in alphabetical order within each SOC.

The number and percentage of subjects experiencing TEAEs will be summarized.

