Such an event can result from use of the drug as stipulated in the protocol, as well as from accidental or intentional overdose, drug abuse, or drug withdrawal. Any worsening of a pre-existing condition or illness is considered an AE. Worsening in severity of a reported AE should be reported as a new AE. Laboratory abnormalities and changes in vital signs are considered to be AEs only if they result in discontinuation from the study, necessitate therapeutic medical intervention, meet protocol-specific criteria (see Section 6.2 regarding toxicity management), and/or if the investigator considers them to be AEs. Worsening SLE including flares will be captured and analyzed via the disease activity forms (SLEDAI, BILAG, CLASI, and SFI) and will be analyzed as part of efficacy. As such, worsening SLE and flares will not be captured as AEs unless they result in serious outcomes.

The investigators will monitor each subject for clinical and laboratory evidence of AE on a routine basis throughout the study. All AEs will be followed to a satisfactory conclusion.

An elective surgery/procedure scheduled to occur during a study will not be considered an AE if the surgery/procedure is being performed for a pre-existing condition and the surgery/procedure has been pre-planned prior to study entry. However, if the pre-existing condition deteriorates unexpectedly during the study (e.g., surgery performed earlier than planned), then the deterioration of the condition for which the elective surgery/procedure is being done will be considered an AE. If the subject undergoes elective surgery, the study drug should be interrupted at least 1 week prior to the planned surgery. If the subject must undergo emergency surgery, the study drug should be interrupted at the time of the surgery. For both elective and emergency surgery, allow reintroduction of study drug once the physician has examined the surgical site and determined that it has healed and there is no sign of infection.

If any of the following events (Table 3) are reported, then the following supplemental report must be completed.

Table 3. Adverse Events Requiring Supplemental Reports

| Adverse Events | Supplemental Report |
|----------------------|---|

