7.4 Statistical Analyses for Safety

All safety analyses will be performed on the Safety Analysis Set.

All treatment-emergent adverse events (TEAEs), SAEs, AEs leading to discontinuation, and AESI will be collected during the study. A TEAE is defined as an event with onset or worsening after the first study dose of study drug and within 30 days after the last dose of study drug administration. The number and percentages of subjects experiencing TEAEs will be tabulated using the Medical Dictionary for Drug Regulatory Activities (MedDRA®) System Organ Class (SOC) and preferred term (PT). Summaries (including percentages and events per 100 patient-years) of SAEs, deaths, AEs leading to discontinuation, and AESI will be provided as well. For selected laboratory and vital sign parameters, mean change from Baseline and the percentage of subjects with evaluations meeting pre-defined criteria for Potentially Clinically Important values will be summarized.

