9.2.2 Adverse Event Overview

The number and percentage of subjects experiencing TEAEs will be summarized by treatment group as specified in Section [6.0](#) and overall.

An overview of AEs will be presented consisting of the number and percentage of subjects experiencing at least one event for each of the following AE categories:

- Any treatment-emergent AE
- Any treatment-emergent AE related to study drug according to the investigator
- Any severe treatment-emergent AE
- Any serious treatment-emergent AE
- Any treatment-emergent AE leading to discontinuation of study drug

- Any treatment-emergent AE leading to death
- TEAE of special interest (AESIs) (as defined in [Appendix B](#))
- Any COVID-19 related AE
- All deaths
- COVID-19 related deaths

Additional AEs may be considered for tabulation/summary based on recommendations from Clinical and Safety as deemed appropriate.

The number and percentage of subjects experiencing at least one event of treatment-emergent AEs will be summarized for each treatment group. In addition, an overview of AEs per 100 patient-years of study exposure will be presented for the AE categories defined above. The number of TEAEs reported, the total number of years of study drug exposure, and the TEAE rate per 100 patient-years will be presented.

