9.2.5 SAEs (Including Deaths) and Adverse Events Leading to Study Drug Discontinuation

SAEs (including deaths) and AEs leading to study drug discontinuation will be summarized by SOC and PT and in listing format.

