9.2.9 Listing of Adverse Events

The following additional summaries of AEs will be prepared.

- Listing of Subjects with Treatment-Emergent AESIs
- Listing of Subjects with Pretreatment SAEs
- Listing of Subjects with Treatment-Emergent SAEs
- Listing of Treatment-Emergent AEs that led to discontinuation of study drug
- Listing of all deaths.

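### An adverse event that began in M19-130 and ends treatment in M20-186 at unchanged severity is missing from the SAP's overview and its 9.2.9 listing of events leading to discontinuation

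*SAP*

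**What the plan says.** SAP 9.2.1 defines a treatment-emergent event for this study as "an adverse event with an onset date that is on or after the first dose of study drug from Study M20-186". The window closes 30 days after the final M20-186 dose. Protocol 7.4 is wider: "A TEAE is defined as an event with onset or worsening after the first study dose of study drug". The SAP does not explain why the worsening limb is gone.

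Three SAP outputs deal with adverse events that end treatment:

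- The overview in 9.2.2 has the row "Any treatment-emergent AE leading to discontinuation of study drug". The same categories feed the overview per 100 patient-years.
- 9.2.9 plans a "Listing of Treatment-Emergent AEs that led to discontinuation of study drug".
- 9.2.5 says that "SAEs (including deaths) and AEs leading to study drug discontinuation will be summarized by SOC and PT and in listing format", with no limit to treatment-emergent events.

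Separately, SAP 5.0 counts every premature stop of study drug by primary reason. SAP 9.1 sets the scope of the safety section: "Safety analyses will include reporting of adverse events, laboratory, and vital signs measurements based on data in Study M20-186". SAP 13.0 puts off integrated summaries to a later submission. Protocol 5.1 admits only subjects who completed M19-130 on study drug.

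**The concern.** Subjects in Groups 1 to 4 stay on the same drug across the two studies. Take an event that starts late in M19-130 on active drug, persists at the same grade, and leads the subject to stop a few weeks into M20-186. In M19-130 the subject completed on drug, so there is no discontinuation. In M20-186 the event is not treatment-emergent, so it is absent from the overview row, from its rate and from the 9.2.9 listing.

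Tolerability is part of the primary objective (protocol 3, SAP 2.1), and adverse events that end treatment are one of its plainest measures. Lasting intolerance that finally ends treatment is something an extension should be able to show. Protocol 4.2 makes each group's safety profile in the randomized study the main point of comparison, and this kind of stop falls between the two studies. The SAP is also uneven. For laboratory and vital-sign changes in subjects already on active drug, 9.1 takes Baseline before M19-130 dosing and so treats exposure as continuous. For adverse events the clock restarts at the first M20-186 dose.

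**Working it through.** The point is definitional, so the main check traces an event through the wording. The arithmetic only shows how much one subject weighs.

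**Trace.** Take an event that began in M19-130 and led to stopping drug in M20-186.

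| Carried-over event | 9.2.2 row and rate | 9.2.9 listing | 9.2.5 table and listing | 5.0 disposition |
|---|---|---|---|---|
| (a) Same severity, onset date known | Not counted | Not listed | Unclear | Stop counted |
| (b) Severity rises after the first M20-186 dose | Counted | Listed | Counted | Stop counted |
| (c) Onset date incomplete, nothing showing earlier onset | Counted | Listed | Counted | Stop counted |

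- Row (b) follows from protocol 6.1: "Worsening in severity of a reported AE should be reported as a new AE". The new record has an onset in M20-186 and meets SAP 9.2.1.
- Row (c) follows from the default in SAP 9.2.1 that treats an incomplete onset date as treatment-emergent unless other evidence shows otherwise.
- Row (a) is the gap. In 9.2.5 the wording would admit the event, but 9.1 confines safety analyses to M20-186 data, and the SAP does not say whether an ongoing M19-130 record falls within that.

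**Plan's own figure.** Protocol 4.1 projects 65 subjects in each of 5 groups: 5 × 65 = 325. SAP 2.4 expects 60% to 80% to roll over: 0.60 × 325 = 195 and 0.80 × 325 = 260. Both stated figures reproduce.

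**Weight of one omitted subject.** Assume equal rollover in every group and a 1:1 split of the placebo subjects (SAP 2.3).

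- Groups 1 to 4: n = 65 × 0.60 = 39 to 65 × 0.80 = 52. One subject is 100/39 = 2.6 to 100/52 = 1.9 percentage points.
- Groups 5a and 5b: n = 39/2 = 19.5 to 52/2 = 26. One subject is 100/19.5 = 5.1 to 100/26 = 3.8 points.

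**Weight of one omitted event in the rate.** SAP 9.2.4 uses 100 × events / patient-years. With full 56-week exposure (392 days), patient-years = n × 392/365.25.

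- Groups 1 to 4: 41.9 to 55.8 patient-years, so one event is 2.4 to 1.8 per 100.
- Groups 5a and 5b: 20.9 to 27.9 patient-years, so one event is 4.8 to 3.6 per 100.

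Full exposure is the most patient-years possible over the planned period, so early stopping would make each event weigh slightly more.

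**The case against.** The case against is substantial, and most of it stands as a limit on the point.

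A reader might infer that such events disappear from every count of discontinuations. The documents do not support that. SAP 9.2.5 tabulates and lists adverse events leading to discontinuation without restricting them to treatment-emergent ones. SAP 5.0 shows every stop by primary reason. A mismatch with the overview would therefore be visible to a careful reader.

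A reader might also infer that the missing worsening limb loses events that get worse. For severity it loses little, because protocol 6.1 turns them into new events. Nor are deaths lost: 9.2.2 has a row for all deaths, 9.2.9 lists them all, and 9.2.5 includes them. The 9.2.9 listing of pretreatment serious events may also recover some serious carry-over events, though not the non-serious ones.

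The remaining population is narrow. Entry requires that no M19-130 discontinuation criterion was met (protocol 5.1) and that the investigator thinks continued therapy appropriate (protocol 4.2). The gap then needs an event acceptable at rollover that never rises in severity, has a known earlier onset, and still ends treatment. It can happen, since protocol 5.5 lets the investigator or subject stop for any reason, but the documents do not show how often.

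Limiting this report to M20-186 data was deliberate, and integrated data are to follow. That means the events need not be lost for good, but it does not repair this study's own tables. Finally, the M19-130 SAP and the text of the Operations Manual are not among the documents, so how ongoing events pass between the databases cannot be checked.

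**Conclusion.** The point holds in a limited form. A carried-over event of unchanged severity and known M19-130 onset that ends treatment in M20-186 is left out of the 9.2.2 row and rate and the 9.2.9 listing. Its place in 9.2.5 is unclear, while disposition counts the stop. The SAP's outputs on the same question can therefore disagree, and the overview can err only toward fewer discontinuations. In Groups 1 to 4 the omitted event would have begun on the same active drug. In Groups 5a and 5b it would have begun on placebo, so there it needs a label, not silent removal.

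The size is unknown. The documents give neither a rate of stopping for adverse events nor a share with earlier onset, so no expected fall in the rate can be derived. What can be said is that the groups are small: under equal 60% to 80% rollover, one subject moves a group's percentage by 1.9 to 2.6 points (Groups 1 to 4) or about 3.8 to 5.1 points (5a and 5b). This also assumes that all groups continue and that ongoing M19-130 events are not re-entered in M20-186 with a new onset date.

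**What to change.** - In SAP 9.2.2, 9.2.5 and 9.2.9, count adverse events leading to discontinuation of M20-186 study drug by the date of that drug action, whatever the onset date. Use the same rule in all three.
- Flag events with onset before the first M20-186 dose, and for Groups 5a and 5b flag onset on placebo, so that readers can separate the two kinds.
- Restore worsening to the definition in SAP 9.2.1 so that it matches protocol 7.4.

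The cost is SAP wording and linking carried-over M19-130 adverse event records to the M20-186 drug action. How much work the linkage takes cannot be judged from these documents. Some reported discontinuation rates would become slightly less favourable. Trial conduct does not change.
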